### 8.3.4 Quality of Life Questionnaire: Short Inflammatory Bowel Disease Questionnaire (SIBDQ)

The SIBDQ is a health-related quality of life (HRQoL) tool measuring physical, social, and emotional status. Scores range between 10 and 70, reflecting poor to good HRQoL. The SIBDQ has been predominantly used in trials for Crohn's disease, and further validation of the SIBDQ is desirable in UC patients. A sample of the SIBDQ is provided in [Appendix 3](#).

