### 9.5 Statistical Analyses

No formal inferential statistics are planned for this study. Descriptive statistics will be calculated to summarize the changes from baseline in the primary and secondary endpoints. Frequency counts will be compiled for qualitative safety analysis.

- Primary Endpoint(s):
  - Change from Baseline in Total Mayo Score at Week 8
- Secondary Endpoint(s):
  - Change from Baseline in Partial Mayo Score at Week 8
  - Change from Baseline in Histologic Assessment of Endoscopic Biopsy at Week 8
  - Change from Baseline in UCEIS Score at Week 8
  - Number and Severity of treatment-emergent AE (TEAEs) up to Week 8
  - Change from Baseline in SIBDQ at Week 8
  - Change from Baseline in Concentration of Biomarkers (serum CRP, fecal calprotectin, and fecal lactoferrin) at Week 8
  - Plasma and Tissue Concentration of BBT-401-1S in Patients with Active UC

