2.2.2 Secondary Endpoints

[figure not shown]
- Change from Baseline in Partial Mayo Score at Week 8
- Change from Baseline in Histologic Assessment of Endoscopic Biopsy at Week 8
- Change from Baseline in Ulcerative Colitis Endoscopic Index of Severity (UCEIS) Score at Week 8
- Change from Baseline in Short Inflammatory Bowel Disease Questionnaire (SIBDQ) at Week 8
- Number and Severity of Treatment Emergent Adverse Events (TEAEs) up to Week 8
- Change from Baseline in Concentration of Biomarkers (C-reactive protein [CRP], fecal calprotectin, and fecal lactoferrin) at Week 8
- Plasma and Tissue Concentration of BBT-401-1S in Patients with Active UC

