4.7.2 Secondary Efficacy Analyses

The secondary efficacy analyses will be based on the mITT set on the following endpoints:

- Change from Baseline to Week 8 in Partial Mayo Score
- Change from Baseline to Week 8 in Histologic Assessment of Endoscopic Biopsy
- Change from Baseline to Week 8 in UCEIS Score
- Change from Baseline to Week 8 in SIBDQ

For each secondary efficacy endpoint described above, descriptive statistics will be presented by treatment and cohort group including mean, SD, median, max, and min. Similar to the primary efficacy analysis, mixed model repeated measures (MMRM) analyses will be performed for various secondary efficacy endpoints as noted above.

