6 LIST OF TABLES AND FIGURES

List of Tables

ICH Heading	Table Number	Table Description
14.1	14.1.1	DEMOGRAPHIC Summary of Patient Disposition (All Patients)
	14.1.2	Summary of Demographic and Baseline Characteristics (mITT Analysis set)
	14.1.3	Summary of Medical History (mITT Analysis set)
	14.1.4	Summary of Prior Medications (mITT Analysis set)
	14.1.5	Summary of Concomitant Medications (mITT Analysis set)
14.2		EFFICACY
14.2.1	14.2.1.1	Primary Efficacy Summary of Change of Total Mayo Score from Baseline to Week 8 (mITT Analysis set)
	14.2.1.2	Summary of Change of Total Mayo Score from Baseline to Week 8 (PP Analysis set)
14.2.2		Secondary Efficacy
	14.2.2.1.1	Summary of Change of Partial Mayo Score from Baseline to Week 8 (mITT Analysis set)
	14.2.2.1.2	Summary of Change of Partial Mayo Score from Baseline to Week 8 (PP Analysis set)

- 14.2.2.2.1 Summary of Change of Histologic Assessment of Endoscopic Biopsy from Baseline to Week 8 (mITT Analysis set)
- 14.2.2.2.2 Summary of Change of Histologic Assessment of Endoscopic Biopsy from Baseline to Week 8 (PP Analysis set)
- 14.2.2.3.1 Summary of Change of Ulcerative Colitis Endoscopic Index of Severity (UCEIS) Score from Baseline to Week 8 (mITT Analysis set)
- 14.2.2.3.2 Summary of Change of Ulcerative Colitis Endoscopic Index of Severity (UCEIS) Score from Baseline to Week 8 (PP Analysis set)
- 14.2.2.4.1 Summary of Change of Short Inflammatory Bowel Disease Questionnaire (SIBDQ) from Baseline to Week 8 (mITT Analysis set)
- 14.2.2.4.2 Summary of Change of Short Inflammatory Bowel Disease Questionnaire (SIBDQ) from Baseline to Week 8 (PP Analysis set)
- 14.2.3 Exploratory Efficacy**
 - 14.2.3.1 Summary of Change of Concentration of Biomarkers from Baseline to Week 8 (mITT Analysis set)
 - 14.2.3.2 Summary of Change of Concentration of Biomarkers from Baseline to Week 8 (PP Analysis set)
- 14.3 SAFETY**
 - 14.3.1 Display of Adverse Events**
 - 14.3.1.1 Overall Summary of Treatment-Emergent Adverse Events up to Week 8 (Safety Analysis set)
 - 14.3.1.2 Summary of Treatment-Emergent Adverse Events up to Week 8 by System Organ Class and Preferred Term (Safety Analysis set)
 - 14.3.1.3 Summary of Treatment-Emergent Adverse Events up to Week 8 by System Organ Class, Preferred Term, and Severity (Safety Analysis set)
 - 14.3.1.4 Summary of Treatment-Emergent Adverse Events up to Week 8 by System Organ Class, Preferred Term, and Relationship to Study Drug (Safety Analysis set)

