95% CI for Differences		(XX.X, XX.X)

Note: Least Squares means, p-values were from MMRM model with treatment and baseline score as fixed effects, and center as random effect. Restricted Maximum Likelihood (REML) with an unstructured variance-covariance matrix is used for estimation in the MMRM analysis.

Table 14.2.2.3.2
 Summary of Change of Ulcerative Colitis Endoscopic Index of Severity (UCEIS) Score from Baseline to Week 8
 PP Analysis set

Study Visit	Placebo (N=XX)	BBT-401-1S (N=XX)
Baseline		
n (missing)	XX (XX)	XX (XX)
Mean (SD)	XX.X (XX.XX)	XX.X (XX.XX)
Median	XX.X	XX.X
Min, Max	XX, XX	XX, XX
Week 8		
n (missing)	XX (XX)	XX (XX)
Mean (SD)	XX.X (XX.XX)	XX.X (XX.XX)
Median	XX.X	XX.X
Min, Max	XX, XX	XX, XX
Change from Baseline to Week 8		
n (missing)	XX (XX)	XX (XX)
Mean (SD)	XX.X (XX.XX)	XX.X (XX.XX)
Median	XX.X	XX.X
Min, Max	XX, XX	XX, XX
LS Mean (SE)	XX.X (XX.XX)	XX.X (XX.XX)
P-Value, Active vs Placebo		0.XXX
LS Mean Difference (SE)		XX.X (XX.XX)
95% CI for Differences		(XX.X, XX.X)

Note: Least Squares means, p-values were from MMRM model with treatment and baseline score as fixed effects, and center as random effect. Restricted Maximum Likelihood (REML) with an unstructured variance-covariance matrix is used for estimation in the MMRM analysis.

Table 14.2.2.4.1
Summary of Change of Short Inflammatory Bowel Disease Questionnaire (SIBDQ) from Baseline to Week 8
mITT Analysis set

Study Visit	Placebo (N=XX)	BBT-401-1S (N=XX)
SIBDQ Question #: xxxxxx		
Baseline		
n (missing)	XX (XX)	XX (XX)
Mean (SD)	XX.X (XX.XX)	XX.X (XX.XX)
Median	XX.X	XX.X
Min, Max	XX, XX	XX, XX
Week 8		
n (missing)	XX (XX)	XX (XX)
Mean (SD)	XX.X (XX.XX)	XX.X (XX.XX)
Median	XX.X	XX.X
Min, Max	XX, XX	XX, XX
Change from Baseline to Week 8		
n (missing)	XX (XX)	XX (XX)
Mean (SD)	XX.X (XX.XX)	XX.X (XX.XX)
Median	XX.X	XX.X
Min, Max	XX, XX	XX, XX
LS Mean (SE)	XX.X (XX.XX)	XX.X (XX.XX)
P-Value, Active vs Placebo		0.XXX
LS Mean Difference (SE)		XX.X (XX.XX)
95% CI for Differences		(XX.X, XX.X)

Note: Least Squares means, p-values were from MMRM model with treatment and baseline score as fixed effects, and center as random effect. Restricted Maximum Likelihood (REML) with an unstructured variance-covariance matrix is used for estimation in the MMRM analysis.

Programming Note: Start a new page for each question.

Table 14.2.2.4.2
 Summary of Change of Short Inflammatory Bowel Disease Questionnaire (SIBDQ) from Baseline to Week 8
 PP Analysis set

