Study Visit	Placebo (N=XX)	BBT-401-1S (N=XX)
SIBDQ Question #: xxxxxxx		
Baseline		
n (missing)	XX (XX)	XX (XX)
Mean (SD)	XX.X (XX.XX)	XX.X (XX.XX)
Median	XX.X	XX.X
Min, Max	XX, XX	XX, XX
Week 8		
n (missing)	XX (XX)	XX (XX)
Mean (SD)	XX.X (XX.XX)	XX.X (XX.XX)
Median	XX.X	XX.X
Min, Max	XX, XX	XX, XX
Change from Baseline to Week 8		
n (missing)	XX (XX)	XX (XX)
Mean (SD)	XX.X (XX.XX)	XX.X (XX.XX)
Median	XX.X	XX.X
Min, Max	XX, XX	XX, XX
LS Mean (SE)	XX.X (XX.XX)	XX.X (XX.XX)
P-Value, Active vs Placebo	0.XXX	
LS Mean Difference (SE)	XX.X (XX.XX)	
95% CI for Differences	(XX.X, XX.X)	

Note: Least Squares means, p-values were from MMRM model with treatment and baseline score as fixed effects, and center as random effect. Restricted Maximum Likelihood (REML) with an unstructured variance-covariance matrix is used for estimation in the MMRM analysis.

Programming Note: Start a new page for each question.

Table 14.2.3.1
 Summary of Change of Concentration of Biomarkers from Baseline to Week 8
 mITT Analysis set

Study Visit	Placebo (N=XX)	BBT-401-1S (N=XX)
Biomarker #1		
Baseline		
n (missing)	XX (XX)	XX (XX)
Mean (SD)	XX.X (XX.XX)	XX.X (XX.XX)
Median	XX.X	XX.X
Min, Max	XX, XX	XX, XX
Week 8		
n (missing)	XX (XX)	XX (XX)
Mean (SD)	XX.X (XX.XX)	XX.X (XX.XX)
Median	XX.X	XX.X
Min, Max	XX, XX	XX, XX
Change from Baseline to Week 8		
n (missing)	XX (XX)	XX (XX)
Mean (SD)	XX.X (XX.XX)	XX.X (XX.XX)
Median	XX.X	XX.X
Min, Max	XX, XX	XX, XX
LS Mean (SE)	XX.X (XX.XX)	XX.X (XX.XX)
P-Value, Active vs Placebo	0.XXX	
LS Mean Difference (SE)	XX.X (XX.XX)	
95% CI for Differences	(XX.X, XX.X)	
Biomarker #2		
...		

Note: Least Squares means, p-values were from MMRM model with treatment and baseline score as fixed effects, and center as random effect. Restricted Maximum Likelihood (REML) with an unstructured variance-covariance matrix is used for estimation in the MMRM analysis.

Programming Note: Start a new page for each biomarker.

Table 14.2.3.2
 Summary of Change of Concentration of Biomarkers from Baseline to Week 8
 PP Analysis set

Study Visit	Placebo (N=XX)	BBT-401-1S (N=XX)
Biomarker #1		
Baseline		
n (missing)	XX (XX)	XX (XX)
Mean (SD)	XX.X (XX.XX)	XX.X (XX.XX)
Median	XX.X	XX.X
Min, Max	XX, XX	XX, XX
Week 8		
n (missing)	XX (XX)	XX (XX)
Mean (SD)	XX.X (XX.XX)	XX.X (XX.XX)
Median	XX.X	XX.X
Min, Max	XX, XX	XX, XX
Change from Baseline to Week 8		
n (missing)	XX (XX)	XX (XX)
Mean (SD)	XX.X (XX.XX)	XX.X (XX.XX)
Median	XX.X	XX.X
Min, Max	XX, XX	XX, XX

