Subject ID	Cohort /Treatment	Visit	Date and Time of Assessment	Q1: How often has the feeling of fatigue or being tired and worn out been a problem for you during the past 2 weeks?	Q2: How often during the last 2 weeks have you delayed or canceled a social engagement because of your bowel problem?	Q3: How much difficulty have you had, as a result of your bowel problems, doing leisure or sports activities you would have liked to have done during the past 2 weeks?	Q4: How often during the last 2 weeks have you been troubled by pain in the abdomen?	Q5: How often during the last 2 weeks have you felt depressed or discouraged?
xx-yyy	xxx/xxx	xxxx	xxxxxx	xxxxxxxx	xxxxxxxx	xxxxxxxx	xxxxxxxx	xxxxxxxx

Subject ID	Cohort /Treatment	Visit	Date and Time of Assessment	Q6: Overall, in the last 2 weeks, how much of a problem have you had with passing large amounts of gas?	Q7: Overall, in the last 2 weeks, how much of a problem have you had maintaining or getting to, the weight you would like to be at?	Q8: How often during the last 2 weeks have you felt relaxed and free of tension?	Q9: How much of the time during the last 2 weeks have you been troubled by a feeling of having to go to the bathroom even though your bowels were empty?	Q10: How much of the time during the last 2 weeks have you felt angry as a result of your bowel problem?
xx-yyy	xxx/xxx	xxxx	xxxxxx	xxxxxxxx	xxxxxxxx	xxxxxxxx	xxxxxxxx	xxxxxxxx

Output ID: <Unique Output id i.e. t-enrol>
<Path/Program Name>

Draft-DDMMYYYY HH:MM:SS

DATE OF DATABASE EXTRACTION: DDMMYYYY
Page 1 of X

Programming note:
For each question, present both numerical and character responses if available.

Listing 16.2.6.6
Biomarker

Subject ID	Cohort /Treatment	Visit	Biomarker Parameter	Date of Sample	Results
xx-yyy	xxx/xxx	xxxx	xxxx	DD-MMM-YYYY/Not Done	xxxxx

Output ID: <Unique Output id i.e. t-enrol> Draft-DDMMYY HH:MM:SS DATE OF DATABASE EXTRACTION: DDMMYY
<Path/Program Name>

Page 1 of X

Programming note: this should include C-reactive protein [CRP], fecal calprotectin, and fecal lactoferrin.

Listing 16.2.7.1
Adverse Events

Subject ID	Cohort /Treatment	AE Term	Description	Severity	Date of Onset/ Resolution	Outcome	Action taken with Study Drug	Relatedness	Is the adverse event serious? (Yes/No)	Seriousness Criteria	Date of Death
xx-yyy	xxx/xxx	xxxx	xxxxxxxxx	xxxx	DD-MMM-YYYY/ DD-MMM-YYYY/ Ongoing	xxxxxxxx	xxxxxxxx	xxxxxx	Yes/No	xxxxxx	DD-MMM- YYYY

Output ID: <Unique Output id i.e. t-enrol>
<Path/Program Name>

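### The SIBDQ tables carry the secondary endpoint's title but analyse ten single questions; no table page or listing column holds the 10 to 70 total

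*SAP*

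**What the plan says.** Protocol 8.3.4 gives the only description of an SIBDQ score in either document: "Scores range between 10 and 70, reflecting poor to good HRQoL". Protocol 9.5 lists "Change from Baseline in SIBDQ at Week 8" among the secondary endpoints. SAP 2.2.2 repeats it as "Change from Baseline in Short Inflammatory Bowel Disease Questionnaire (SIBDQ) at Week 8". SAP 4.7.2 then assigns descriptive statistics and an MMRM to "Change from Baseline to Week 8 in SIBDQ". Each time it is one endpoint, with no mention of items.

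SAP Section 6 plans two SIBDQ tables, 14.2.2.4.1 for the mITT set and 14.2.2.4.2 for the PP set, and both carry the endpoint's name. In the shells, the only block is headed by question number ("SIBDQ Question #: xxxxxxx" in the PP table, and the same heading in the mITT table). The programming note under each reads "Programming Note: Start a new page for each question". Every page has its own LS means, p-value, difference and 95% CI.

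Listing 16.2.6.5 has columns for questions 1 to 10 and nothing after them. Its programming note says "For each question, present both numerical and character responses if available". The Total Mayo, Partial Mayo and UCEIS listings each end with a score column.

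**The concern.** A programmer who follows these shells will not produce the result that the protocol and SAP name as a secondary endpoint. The tables will look complete because they carry its title.

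The ten item pages do not stand in for the total. Raw item means add up to the mean total only if the same patients answer every item and all items run in the same direction. The SD, median, p-value and CI of the total cannot be recovered from the item pages. In general neither can the LS mean difference, because each item model adjusts for its own baseline and estimates its own centre effect. The total would have to be rebuilt from item responses, under scoring choices that neither document states. If that happened after unblinding, the choices would be made with treatment known.

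A second, smaller consequence is that ten unadjusted p-values appear where one endpoint result belongs.

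**Working it through.** **1. What the 10 to 70 range means.** Protocol Appendix 3 has 10 questions with 7 answer options each. It prints no numeric codes, so the coding has to be inferred:

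- sum of items coded 1 to 7: 10 × 1 = 10 to 10 × 7 = 70, which reproduces the protocol's range
- sum of items coded 0 to 6: 0 to 60, which does not
- mean of items coded 1 to 7: 1 to 7, which does not

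Of these, only the sum of ten items coded 1 to 7 and aligned gives the stated range and direction. A single question under that coding spans 1 to 7, so no page in the shells can show the 10 to 70 score.

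**2. Whether the total appears elsewhere.** The table list has no other SIBDQ table, and the listing has no total column. The histology and biomarker shells are also split into pages, but neither document describes those as one score.

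**3. Item direction.** In Appendix 3, question 8 (feeling relaxed) prints its best answer first. The other nine print the worst answer first. If every item were coded in printed order and summed without reversing question 8:

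- best possible patient: 9 × 7 + 1 = 64, not 70
- worst possible patient: 9 × 1 + 7 = 16, not 10

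The eCRF codes are not shown. This is therefore a reason to check the coding and does not show an error.

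**4. Number of models.** Items: 10 × 2 analysis sets = 20. Total: 1 × 2 = 2. This is for the single active-versus-placebo comparison in the cohort 1 shells.

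**5. Share of the printed p-values (mITT efficacy shells).**

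| | Total Mayo | Partial Mayo | UCEIS | Biomarkers | SIBDQ | Sum |
|---|---|---|---|---|---|---|
| As drafted | 1 | 1 | 1 | 3 | 10 | 16 |
| With the total | 1 | 1 | 1 | 3 | 1 | 7 |

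SIBDQ items supply 10/16 = 62.5%. Histology is left out because its number of tests is not given, and adding it would lower the share. Biomarkers are counted because their shells print p-values, although SAP 4.9 plans no formal analysis of them. Without them the count is 10 of 13.

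**6. Chance findings.** Inputs: two-sided 0.05 (SAP 4.1) and no multiplicity adjustment (SAP 4.14). Assume no drug effect and each test at its nominal level.

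- expected number below 0.05: 10 × 0.05 = 0.5 for the items and 0.05 for one total, whatever the correlation
- at least one of ten, items independent: 1 − 0.95^10 = 0.401
- at least one of ten, any dependence: at most 10 × 0.05 = 0.50

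Positive correlation between items, which is likely within one questionnaire, brings the chance below 0.401.

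**The case against.** The best defence is that the SAP text already commits to analysing the SIBDQ endpoint, and nothing in it replaces the endpoint with item analyses. On this view the defect is a layout gap in shells that SAP Section 1 says were made for cohort 1. SAP 4.1 also requires derived data to be listed, so a total would be listed once derived. The protocol's range and direction fix the sum in practice. UCEIS has no printed sum rule either, and nobody doubts its score. The study is unpowered, the protocol plans no formal inference, and Protocol 8.3.4 itself says the instrument needs further validation in UC.

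Much of this stands, and it limits the severity. No item data are lost, and deriving the total takes one line of code. The error rates in step 6 describe noise in a descriptive study and are not the main point.

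It does not remove the defect. The listing rule in SAP 4.1 applies to derived data, and no text derives a total. The UCEIS comparison works against the defence, because its table analyses the score and its listing has a score column. The shells are marked as a final version, and their instruction to page by question is explicit. Anyone following it produces no endpoint result.

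**Conclusion.** The concern holds. The plan names one SIBDQ endpoint and specifies two tables under its title. Those tables, as drafted, hold ten item analyses each and none of the total. This is an explicit instruction that gives the wrong output, and the missing scoring statement adds to it.

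The conclusion rests on two readings. One is that SIBDQ in the endpoint text means the 10 to 70 score, which is the only SIBDQ score either document describes. The other is that the shells' reference to each question means the ten questions shown in Appendix 3 and Listing 16.2.6.5.

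The change should be made, but it is not critical. This is one secondary endpoint in a descriptive study, and no decision depends on its p-values.

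**What to change.** - **SAP 4.7.2:** state that the endpoint is the change from baseline to Week 8 in the SIBDQ total, defined as the sum of ten items coded 1 to 7, all aligned so that higher is better, with range 10 to 70.
- **Item 8:** check its eCRF coding, and reverse it only if it is not already aligned.
- **Missing items:** set the total to missing at a visit if any item is missing, in line with the no-imputation rule in SAP 4.5 and 4.12. With four placebo patients per cohort, one incomplete form at baseline or Week 8 removes a quarter of that arm's data for this endpoint, so report how many totals are lost this way.
- **Tables 14.2.2.4.1 and 14.2.2.4.2:** make the total the analysed variable. Item pages may stay as descriptive output.
- **Listing 16.2.6.5:** add a total column.

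The cost is one SAP paragraph, one derived variable, two shell edits and one listing column. All items are already collected, so nothing changes for sites or patients.

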BLQ	Below the Lower level of Quantification
CFR	Code of Federal Regulations
CONSORT	Consolidated Standards of Reporting Trials
CRF	Case Report Form
CRP	C-Reactive Protein
DP	Drug Product
ECG	Electrocardiogram
eCRF	Electronic Case Report Forms
FDA	Food and Drug Administration
GCP	Good Clinical Practice
GLP	Good Laboratory Practices
GMP	Good Manufacturing Practices
HBsAg	Hepatitis B Surface Antigen
HIV	Human Immunodeficiency Virus
HRQoL	Health-related Quality of Life
IB	Investigator's Brochure
ICH	International Conference on Harmonisation
IND	Investigational New Drug Application
ICF	Informed Consent Form
IRB	Institutional Review Board
ITT	Intent-To-Treat
MAD	Multiple Ascending Dose
MedDRA	Medical Dictionary for Regulatory Activities
mITT	Modified Intent-To-Treat
PD	Pharmacodynamics
PI	Principal Investigator
PK	Pharmacokinetics
QC	Quality Control
SAE	Serious Adverse Event
SAP	Statistical Analysis Plan
SFU	Safety Follow-Up
SIBDQ	Short Inflammatory Bowel Disease Questionnaire
SMC	Safety Monitoring Committee
SOC	System Organ Class
SOP	Standard Operating Procedure
TEAE	Treatment-Emergent Adverse Event
UC	Ulcerative Colitis
UCEIS	Ulcerative Colitis Endoscopic Index of Severity
ULN	Upper Limit of Normal

1 REVISION HISTORY

SAP Version 1.0 was created and approved prior to any unblinding to the study team.

SAP Version 2.0 was planned to update a statistician of KCRN Research and Section 6 List of Tables and Figures. TFL shells were created for the 1st cohort and attached.

2 STUDY OBJECTIVES AND ENDPOINTS

2.1 Study Objectives

2.1.1 Primary Objective

The primary objective is to assess the efficacy and safety of multiple oral doses of BBT-401-1S in patients with active UC.

2.1.2 Secondary Objectives

The secondary objectives are to assess the plasma and tissue concentration of multiple oral doses of BBT-401-1S in patients with active UC and to evaluate the effects of BBT-401-1S on biomarkers.

2.2 Study Endpoints

2.2.1 Primary Endpoints

- Change from baseline in Total Mayo Score at Week 8

2.2.2 Secondary Endpoints

[figure not shown]
- Change from Baseline in Partial Mayo Score at Week 8
- Change from Baseline in Histologic Assessment of Endoscopic Biopsy at Week 8
- Change from Baseline in Ulcerative Colitis Endoscopic Index of Severity (UCEIS) Score at Week 8
- Change from Baseline in Short Inflammatory Bowel Disease Questionnaire (SIBDQ) at Week 8
- Number and Severity of Treatment Emergent Adverse Events (TEAEs) up to Week 8
- Change from Baseline in Concentration of Biomarkers (C-reactive protein [CRP], fecal calprotectin, and fecal lactoferrin) at Week 8
- Plasma and Tissue Concentration of BBT-401-1S in Patients with Active UC

3 STUDY DESIGN

3.1 Summary of Study Design

This randomized, placebo-controlled, dose-escalation, multicenter, Phase 2 study consists of three cohorts with 16-week treatment period per cohort that will be conducted sequentially. The first cohort will receive 400 mg of BBT-401-1S (starting dose). Efficacy, safety, and PK data of the first cohort will be used to select the dose of the subsequent cohort. For the 1st or 2nd cohort, if the 12th patient (75%) completes Visit 4 (Week 8), unblinding of 12 patients will be performed within 2 weeks after Visit 4 (Week 8) and the unblinding information will be only provided to the Sponsor for the analysis to determine the dose of the next cohort. A dose level may be repeated or added based on the results of the previous cohort(s).

Patients will receive a daily oral dose of BBT 401-1S or placebo for the 16 weeks. While patients who are assigned to Active Group will receive BBT-401-1S for the first 12 weeks and then placebo for the last 4 weeks, patients who are assigned to Placebo Group will receive placebo for the first 8 weeks and then BBT-401-1S for last 8 weeks.

The schedule of assessments is illustrated in Table 1.

Table 1. Schedule of Assessments

	Screening	Treatment Period						SFU
		V2	V3	V4	V5	V6	ET	
Visit Number	V1							
Visit Period	Up to W-4	Baseline	W4	W8	W12	W16	N/A	W2 from LD
Visit Window	N/A	Within 28 days from V1	±3 days	±3 days	±3 days	±3 days	N/A	+ 7 days from LD
Informed Consent	X							
Demographic Information	X							
Medical/medication History	X	X						
Inclusion/exclusion Criteria	X	X						
Vital Signs	X	X	X	X	X	X	X	X
Physical Examination	X	X ^a	X	X	X	X	X	
12-lead ECG	X	X ¹	X	X	X	X	X	
Clinical Lab Tests and Serum Biomarker ²	X	X ^a	X	X	X	X	X	X
Endoscopy (biopsy)	X			X			X ³	
Randomization		X						
Mayo Score	X	X	X	X	X	X	X	
Ulcerative Colitis Endoscopic Index of Severity	X			X			X ^c	
Short Inflammatory Bowel Disease Questionnaire			X	X	X	X	X	
Fecal Biomarker ⁴			X	X	X	X	X	
Plasma Pharmacokinetics ⁵			X	X	X			
Tissue Concentration ⁶	X			X			X ^c	
Drug Dispensing (with subject diary)		X	X	X	X			
Drug Return and Compliance			X	X	X	X	X	
AE and Concomitant Medication		X	X	X	X	X ^g	X ^g	X

AE = adverse event; ECG = electrocardiogram; SFU = Safety Follow-Up; V = Visit; W = Week; ET = Early Termination; LD = Last Dose

¹ Waived if the screening visit is conducted within 10 days prior to Visit 2 (Baseline).

² Serum chemistry, hematology, coagulation test, HIV and hepatitis screens, serum hCG (women with childbearing potential only), and serum CRP (not measured at SFU).

³ Only if early termination occurs before Visit 4 (W8).

⁴ Fecal calprotectin and fecal lactoferrin. A collection container will be dispensed to patients on the previous visit.

⁵ Visit 2 (Baseline) and Visit 3 (W4): pre-dose and 3 and 6 hours post-dose; Visit 4 (W8): pre-dose only.

⁶ During the endoscopy (flexible proctosigmoidoscopy/colonoscopy) for biopsy.

^g Reviewing any changes in smoking habits of subject during the study period.

